5.3 Interventions

Intervention: LTOT prescribed for 24 h/day.

Control: LTOT prescribed for 15 h/day. The patient is instructed to use LTOT during sleep and to not use LTOT for a total 9 hours during daytime.

Treatment duration: From the date of randomization to 12 months after randomization (end of trial).

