7.8 Evaluation of safety

Adverse events will be presented as plain text in a listing. If applicable, the number of adverse events will be compiled per treatment group in a frequency table. No statistical test between the treatment groups will be performed.

8 Analysis data base definitions

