* Self-reported oxygen use is defined as mean hours/day. If missing, we will use mean h/day last week, using the questionnaire at 12 months, or (if missing) 3 months. (Duration=number of hours per day)

**t-test for mean difference

Table 12 Adverse events (PP and ITT)

Table 12.1 Adverse events

This table will be constructed if there is enough data.

	LTOT 15h/day n=	LTOT 24h/day n=	Total n=
Number of patients with AE (Total number of AE)	n[n]	n[n]	n[n]
Number of patients with SAE (Total number of SAE)	n[n]	n[n]	n[n]
Number of patients with possibly related AE (Number of possibly related AE)	n[n]	n[n]	n[n]
Number of patients with probably related AE (Number of probably related AE)	n[n]	n[n]	n[n]
Number of patients with unrelated AE (Number of unrelated AE)	n[n]	n[n]	n[n]
Number of AE with maximum intensity=MILD	n	n	n
Number of AE with maximum intensity=MODERATE	n	n	n
Number of AE with maximum intensity=SEVERE	n	n	n
Number of patients with maximum AE intensity=MILD	n	n	n
Number of patients with maximum AE intensity=MODERATE	n	n	n
Number of patients with maximum AE intensity=SEVERE	n	n	n

Table 12.2 Time to adverse events

		LTOT 15h/day n=	LTOT 24h/day n=	Total n=
Time to adverse events (all adverse events)	n			
	Mean (SD)			
	Median (IQR)			
	Min-Max			

2 Figures

NOTE: All figures below are based on dummy data

Figure 1 [Figures for inclusion over time](#)

Figure 1.1 Cumulative enrollment over time in the study (all randomized patients)

[figure not shown]

Figure 1.2 Cumulative enrollment over time in the study (by treatment)

If applicable

Figure 1.3 Cumulative enrollment over time in the study (by site)

If applicable

Figure 1.4 Cumulative enrollment over time in the study (by subgroup)

If applicable

Figure 1.5 Histogram with number of included patients by site and by treatment group

[figure not shown]

Figure 1.6 Reasons why the screened patients were not included in the study

[figure not shown]

Figure 1.7 Kaplan-Meier figure: Time from start until the patient stops being treated

A figure will be constructed and presented by treatment arm. Patients who stop being treated with oxygen before one year will be censored at this time.

Figure 2 CONSORT flow chart

* A patient is correctly randomized if he or she fulfills the inclusion criteria but not the exclusion criteria, has signed informed consent and has been randomized in Swedevox within four weeks of starting LTOT.

**All registry data available except for withdrawals

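### Table 12.2 summarises only the times of adverse events that occurred, so its mean and median say almost nothing about frequency, and no adverse-event output accounts for time at risk

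*SAP*

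**What the plan says.** Section 7.8 sets out three things about adverse events. A listing is always made: "Adverse events will be presented as plain text in a listing". Counts are conditional: "If applicable, the number of adverse events will be compiled per treatment group in a frequency table". There is no inference: "No statistical test between the treatment groups will be performed".

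The output shells (Appendix 2) add two tables. Table 12.1 gives, by arm, "Number of patients with AE (Total number of AE"), followed by SAEs, relatedness and intensity. It carries the note "This table will be constructed if there is enough data". Table 12.2 gives "Time to adverse events (all adverse events") by arm and in total, with rows for n, mean (SD), median (IQR) and min-max. It carries no such condition.

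The treatment period in section 5.3 runs "From the date of randomization to 12 months after randomization (end of trial"). The derived-variables appendix defines times to death, hospitalization, the composite and treatment stop. It does not define time to adverse event, so neither the time origin nor the handling of repeat events is stated.

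Tables 5.13 to 5.24, by contrast, give person-years and events per 100 patient-years with 95% CI for the composite, mortality and hospitalization outcomes.

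**The concern.** A table headed as time to event and laid out by arm invites the reader to compare the arms on it. The average time of the events that occurred is not a measure of risk. An arm with many more adverse events can have the same average time as an arm with few, because patients who never had an event are left out and not treated as censored. The average also depends on how long patients stay alive, since events late in the year can only be recorded in survivors.

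At stake is whether the safety output can answer the ordinary question of how often adverse events occur per unit of time under each prescription. Table 12.2 is the only adverse-event table that uses time, and it does not answer that question. Table 12.1 gives counts without a person-time denominator, and it may not be produced.

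**Working it through.** **Inputs.** Follow-up is 365 days (sections 5.3 and 7.5). The planned total is 230 with 1:1 allocation (section 9.2), so 115 per arm. The SAP states no adverse-event rate and no mortality figure, so there is no adverse-event figure of its own to reproduce. Rates of 0.1 to 1 per patient-year in one arm and three times that in the other are assumed, with death hazard 0 or 0.4 per year.

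**1. All events pooled, constant rate r.** The expected number of events at time t is proportional to r × S(t), where S is the survival curve. The mean event time is therefore

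∫ t·r·S(t) dt / ∫ r·S(t) dt = ∫ t·S(t) dt / ∫ S(t) dt,

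and r cancels. Without deaths this is 365/2 = 182.5 days. With hazard 0.4 per year, ∫ S = (1 − e^−0.4)/0.4 = 0.824 and ∫ t·S = (1 − 1.4·e^−0.4)/0.16 = 0.385. The mean is 365 × 0.385/0.824, about 170 days, at any rate.

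Simulation with 115 patients per arm and 600 replicates agrees:

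| Death hazard | Rates per patient-year | Mean event time, days | Number of events |
|---|---|---|---|
| 0 | 0.1 vs 0.3 | 184.9 vs 182.1 | 11.5 vs 34 |
| 0 | 0.5 vs 1.5 | 182.7 vs 182.2 | 58 vs 173 |
| 0 | 1 vs 3 | 183.2 vs 182.8 | 115 vs 345 |
| 0.4 | 0.5 vs 1.5 | 170.7 vs 170.8 | 47 vs 142 |

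The medians behave alike: 183.3 vs 181.7 days at 0.5 vs 1.5 without deaths. The time summary does not separate the arms. The event count does, threefold.

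**2. First event per patient only.** The shell could also be programmed this way. Among patients with an event by one year, and without deaths, the mean is 365 × [1/r − e^−r/(1 − e^−r)]. This gives 179 vs 173 days at 0.1 vs 0.3, 167 vs 138 at 0.5 vs 1.5, and 153 vs 103 at 1 vs 3. It does respond to the rate, but weakly when events are sparse, and event-free patients are still left out.

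**3. What a rate would show.** At 0.5 vs 1.5 without deaths, person-time is 115 years per arm. The rates are 58/115 and 173/115, or about 50 and 150 per 100 patient-years. Patients with at least one event number 115 × (1 − e^−0.5) = 45 and 115 × (1 − e^−1.5) = 89.

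**4. How much time at risk could differ.** With constant hazard and one-year mortality m, mean person-time is m/(−ln(1 − m)) years. For an assumed m of 20% vs 40% this is 0.90 vs 0.78. Equal rates would then give about 13% fewer events in the arm with higher mortality (0.783/0.896 = 0.87). With equal mortality there is no distortion.

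**The case against.** The strongest reply is that frequency is the task of Table 12.1 and that Table 12.2 only describes when events happened. A reader might infer from the arithmetic above that a threefold difference in adverse-event rate would look like no difference in the report. The documents do not support that. Table 12.2 has an n row, which would read about 58 vs 173 in the example if n counts events. Table 12.1 and the frequency table in section 7.8, when produced, give counts by arm, and the listing shows every event. This part of the reply stands.

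A reader might also infer that the 80% event rate in section 9.2 implies much lost time at risk. It does not: that figure is death or first hospitalization combined, and hospitalization does not end observation for adverse events. The SAP gives no mortality figure.

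Three further replies carry weight:
- On a first-event reading the mean does respond to the rate.
- The effect of survival on the pooled mean is small. Going from an assumed 20% to 40% mortality moves it by about 9 days (about 176 to 167), while with 35 events and an SD of about 105 days the standard error is 105/√35, about 18 days.
- A reader could divide the Table 12.1 counts by the person-years in Tables 5.19 and 5.20 and obtain a close rate.

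What these replies do not remove is that the mean and median rows answer no safety question about the arms, that the counts are conditional while these rows are not, and that no adverse-event output itself relates events to time at risk.

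**Conclusion.** The point holds in a limited form. The mean and median in Table 12.2 are close to uninformative about adverse-event frequency, exactly so when all events are pooled at a constant rate. The output as a whole would not conceal a large difference, because counts appear elsewhere when those tables are produced. The gap is that the only adverse-event table using time ignores event-free patients, censoring and competing death. The table is also under-defined: pooled and first-event readings give about 182 and 138 days at 1.5 events per patient-year.

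The sizes rest on assumed rates, constant hazards and 115 patients per arm. This is a minor reporting weakness. It affects no primary or secondary efficacy conclusion.

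**What to change.** Replace the Table 12.2 summary with two descriptive outputs by arm:

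1. Adverse-event and SAE rates per 100 patient-years with 95% CI. Person-time runs from randomization to death, study withdrawal or day 365. The person-years in the all-cause mortality rows of Tables 5.19 (ITT) and 5.20 (PP) can be reused, with follow-up also ended at study withdrawal.
2. Cumulative incidence of the first adverse event, with death as a competing event, as section 7.6 already does for hospitalization.

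Add time to first adverse event to the derived variables, with randomization as origin. Name the analysis set: Table 12 is headed PP and ITT, whereas section 6.3 assigns adverse events to the safety population, and the person-years must match the set used. No test is added, so section 7.8 stands.

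The cost is a shell edit with no new data. The downside is imprecision if routine care yields few reports. With 12 events in 115 patient-years the rate is 10.4 per 100, with an approximate Poisson 95% CI of 10.4 × exp(±1.96/√12), or 5.9 to 18.4, and wider still if events cluster within patients.

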The purpose of this plan is to give a complete and detailed description of the statistical analyses and the descriptive statistics that will be included in the report for the study REDOX. This SAP is based on protocol version “200122 REDOX Final Study Protocol v1.8_FINAL” The study biostatistician at Uppsala Clinical Research Center (UCR) is responsible for the writing of the plan and the execution of the statistical analyses. The results will be presented according to the output specification (see Appendix 2 Output Shells). This plan is completed prior to un-blinding/closing of the study database. The study report will include the analyses of the primary endpoint and secondary objectives concerning the primary endpoint. Following secondary objectives will not be analyzed and reported at UCR:

Compared to patients with LTOT prescribed for 15 h/day, does continuous oxygen therapy 24 h/day:

- Fail to reduce the rate of an incident diagnosis of cardiovascular disease?
- Fail to reduce the level of breathlessness?
- Fail to reduce fatigue?
- Fail to improve level of self-reported physical activity?
- Fail to improve health-related quality of life (HRQOL)?
- Fail to improve cognition?
- Fail to increase the patient’s preference in continuing LTOT?

The statistical methods for the above are described in this plan, in order to be outlined before the analysis database is un-blinded and locked. However, these will be analyzed subsequently by the Sponsor Region Blekinge.

2 SAP version history

Version	Date	Reason for change
1.1	2023-04-05	
1.2	2023-04-06	See previous version
1.3	2023-04-24	See previous version

3 Abbreviations and definitions

Different patient groups will be used in the tabulations. The group *All randomized patients* consists of all patients who have fulfilled all the inclusion criteria but not any of the exclusion criteria, submitted signed informed consent to participate in the study and thereby received a patient number (=randomization number). Incorrectly registered patients are not included.

Screened subject	Patients who has signed the Informed Consent Form (ICF)
Randomized subjects	Patients who have fulfilled eligibility criteria and have been randomized
Screening failure	Patients that have been screened but have not been randomized, will be considered as screen failures
Withdrawals	Patients that were randomized but did not complete the study
Discontinued	Patients who discontinued LTOT

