4.1.2 Secondary objectives

Compared to patients with LTOT prescribed for 15 h/day, does continuous oxygen therapy 24 h/day: (underlined objectives will be analyzed and reported by UCR)

- Fail to reduce the mortality rate from all causes?
- Fail to reduce hospitalization rate from all causes?
- Fail to reduce mortality rate from respiratory disease?
- Fail to reduce mortality rate from cardiovascular disease?
- Fail to reduce hospitalization rate from respiratory disease?
- Fail to reduce hospitalization rate from cardiovascular disease?
- Fail to reduce the rate of an incident diagnosis of cardiovascular disease?
- Fail to reduce the level of breathlessness?
- Fail to reduce fatigue?
- Fail to improve level of self-reported physical activity?
- Fail to improve health-related quality of life (HRQOL)?
- Fail to improve cognition?
- Fail to increase the self-reported oxygen utilization?
- Fail to decrease the rate of LTOT withdrawal?
- Fail to increase the patient's preference in continuing LTOT?

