4.2.2 Secondary outcome variables

- Mortality rate from all causes at 3 and 12 months
- Mortality rate from respiratory disease at 3 and 12 months
- Mortality rate from cardiovascular disease at 3 and 12 months
- Hospitalization rate from all causes at 3 and 12 months
- Hospitalization rate with a primary diagnosis of respiratory disease or respiratory infection at 3 and 12 months
- Hospitalization rate with a primary diagnosis of cardiovascular disease at 3 and 12 months
- Rate of an incident diagnosis of cardiovascular disease at 3 and 12 months

Self-reported questionnaire data collected at 3 and 12 months:

- Self-rated oxygen utilization
- Breathlessness (Multidimensional Dyspnea Profile; MDP)
- Fatigue (FACIT-Fatigue)
- Informant-rated cognition (IQCODE and FAQ)
- Self-rated cognition (BAS)
- Health-related quality of life (CAT and EQ5D-5L)
- Global impression of change from baseline (GIC)
- Self-reported physical activity
- Preference of continuing treatment

5 Study design

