5.6 Study outline

- Patient starting LTOT
- Inclusion/exclusion criteria
- Written consent
- Randomization in Swedevox at or within four weeks of starting LTOT
- Questionnaire three months after randomization, including self-reported adherence
- Study end at 1 year after randomization:
 - Primary endpoint of all-cause mortality or hospitalization
 - Secondary endpoints (registries and 12-month questionnaire, including self-reported adherence)

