5.7 Study assessments

Item	Baseline	3 months	1 year (study end)
Swedevox Register			
Demographics	X		
Height and weight	X		
Spirometry	X		
Blood gases on air and oxygen	X		
Primary and secondary causes of starting LTOT	X		
Oxygen dose, equipment and duration	X		
Use of long-term mechanical ventilator	X		X
Date and reason of LTOT withdrawal		X	X
Causes of Death Register			
Date, place, and causes of death		X	X
Patient Register			
Diagnoses / comorbidity and procedures	X	X	X
Hospitalizations	X	X	X
Prescribed Drug Register			
Dispensed drug prescriptions	X	X	X
Clinical visits			
Adverse events		(X) ^a	(X) ^a
Patient questionnaire			
Self-reported oxygen utilization		X	X
Breathlessness (MDP; NRS of worst; refractory; mMRC)		X	X
Fatigue (FACT-Fatigue)		X	X
Self-reported physical activity (modified Grimby questionnaire)		X	X
Cognitive questionnaires (BAS, IQCODE and FAQ)		X	X
HRQOL (EQ5D-5L and CAT)		X	X
Global impression of change (GIC)		X	X
Treatment preference		X	X

^aAdverse events will be collected at the patient's ordinary clinical visits.

6 Definition of analysis populations

As non-adherence to the allocated treatment might cause a potential bias towards equivalence between treatments, in which analysis according to the intention to treat (ITT) principle would not be conservative, all endpoints will be analyzed according to both the ITT and the Per Protocol (PP) principle in the subpopulations stated in section 6.3.

The classification of study patients into different analysis populations will be performed after the unblinding of treatment allocation to the analyst.

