*Socialstyrelsen will provide us with the date of event. Time to event (in days) will be calculated by UCR

*Time to composite event (All-cause mortality/ All-cause Hospitalization)	Included in the order from Socialstyrelsen
*Time to all-cause mortality	Included in the order from Socialstyrelsen
*Time to 1st hospitalization	Included in the order from Socialstyrelsen
Mortality from respiratory disease	respiratory disease or infection (A40; J00-J99)
Mortality from cardiovascular disease	Underlying cause of death (UCD) heart disease (I00-I99)
Hospitalization from respiratory disease	UCD respiratory disease or infection (A40; J00-J99)
Hospitalization from cardiovascular disease	UCD heart disease (I00-I99)
Time to Mortality from respiratory disease	Death (from respiratory disease) date – Study start date
Time to Mortality from cardiovascular disease	Death (from cardiovascular disease) date – Study start date
Time to Hospitalization from respiratory disease	Date of hospitalization from respiratory disease – Study start date
Time to Hospitalization from cardiovascular disease	Date of hospitalization from cardiovascular disease – Study start date
Time from start until the patient stops being treated	End of treatment – Date for start of treatment
Discontinued LTOT	From Swedevox Registry
Withdrawals	DATE_OF_LTOT_WITHDRAWAL REASON_W
ITT	All randomized patients that start LTOT
PP	A randomized patient will be excluded from the PP set if LTOT has been discontinued before the primary outcome assessment or the mean LTOT utilization during follow-up to the primary endpoint is below 20 h/day for the 24 h/day group, and below 13 h/day or above 17 h/day in the LTOT 15 h/day group
COPD	J44; exacerbation: J44.0 and J44.1
Heart disease	I00-I99
Respiratory disease or infection	A40; J00-J99
fev1/fvc	FEV1/FVC
BMI	WEIGHT(kg)/(HEIGHT (m)*HEIGHT (m))
Age	Round down (RANDOMIZATION_DATE - DATE_OF_BIRTH)/365.25
Duration of treatment	Number of days with treatment during the study
Self-rated hours of oxygen	Self-reported oxygen use (mean hours/24h) is categorized using 1) average use since starting LTOT, or (if missing) mean h/day last week; using the

	questionnaire at 12 months, or (if missing) 3 months (and the described algorithm used for each time point).
Subgroup 1 Participants with more severe resting hypoxemia at LTOT start	PaO ₂ < 7.4 kPa breathing air
Subgroup 2 Participants with more moderate hypoxemia at LTOT start	PaO ₂ 7.4–8.0 kPa breathing air

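### The LTOT-withdrawal objective has no named outcome or between-arm analysis, and its only time-to-event output (Figure 1.7) censors patients when they stop

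*SAP*

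**What the plan says.** Section 4.1.2 asks whether continuous oxygen does the following, compared with 15 h/day: "Fail to decrease the rate of LTOT withdrawal". The SAP's opening section has a list introduced by "Following secondary objectives will not be analyzed and reported at UCR". Its seven items are cardiovascular incidence, breathlessness, fatigue, physical activity, quality of life, cognition and treatment preference. LTOT withdrawal is not among them.

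The data exist. The assessment schedule in section 5.7 has a Swedevox row, "Date and reason of LTOT withdrawal", at 3 months and 1 year. The Derived Variables appendix holds a discontinuation flag, a withdrawal date and reason, and a duration defined as "Time from start until the patient stops being treated End of treatment – Date for start of treatment".

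The planned output is descriptive:
- Table 1: numbers discontinuing LTOT, by arm and reason.
- Section 7.4: completion, or the reason for not completing, by arm.
- Table 8: days of treatment.
- Listing 5: patients who discontinued.
- Figure 1.7: a Kaplan-Meier plot by arm, titled "Time from start until the patient stops being treated", with the note "Patients who stop being treated with oxygen before one year will be censored at this time".

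**The concern.** A Kaplan-Meier curve steps down only at events. Figure 1.7 names stopping as what it measures and then removes each early stop as a censored observation. A programmer who follows the note literally produces a figure that cannot show what its title promises.

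No other part of the plan supplies an inferential answer to the objective, because withdrawal never becomes a named endpoint. This also affects how the main result is read. Section 7.5 treats LTOT withdrawal in three different ways according to its reason, and section 6.2 removes patients who discontinue from the per-protocol set. A reader of a non-superiority claim will want to see when, and in which arm, patients stopped.

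**Working it through.** The SAP states no rate, effect size or power for LTOT withdrawal, so there is no figure to reproduce. The check has four parts.

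**1. Tracing the objective through the plan**

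| Place in SAP | What it holds on LTOT withdrawal |
|---|---|
| 4.1.2 | Listed as a secondary objective |
| 4.2.2 | Nothing; the registry outcomes end with "Rate of an incident diagnosis of cardiovascular disease at 3 and 12 months", and the nine questionnaire items do not include it |
| 7.6 | Not named under Fine-Gray, t-test or chi-square |
| Tables 5, 9, 11 | No row |
| Figure 4 (Kaplan-Meier for outcomes) | Covers listed outcomes only, so not this one |
| Table 1, 7.4, Table 8, Listing 5 | Descriptive only |

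By contrast, the objective just before it in 4.1.2, self-reported oxygen use, has an outcome variable, rows in Table 9 and its own Table 11.7.

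**2. The Figure 1.7 rule in numbers**

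The product-limit estimate is S(t) = product over times up to t of (1 − d/n), where d is the number of events and n the number at risk.

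Inputs: 115 patients per arm (planned total 230, allocated 1:1, section 9.2). The one-year stopping proportions are assumptions, with no deaths in the illustration.

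- *As written:* stops are censored, so d = 0 at every time and S(365) = 1.000.
- *Stop as event:* nobody is censored before day 365, so S(365) = 1 − stops/115.

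| Assumed stops, 24 h vs 15 h | Whole patients | S(365), stop as event | S(365), as written |
|---|---|---|---|
| 10% vs 20% | 12 vs 23 | 0.896 vs 0.800 | 1.000 vs 1.000 |
| 20% vs 30% | 23 vs 34 | 0.800 vs 0.704 | 1.000 vs 1.000 |
| 30% vs 50% | 34 vs 58 | 0.704 vs 0.496 | 1.000 vs 1.000 |

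Arm differences of 0.096, 0.096 and 0.208 all become zero. The result follows from the coding and not from the assumed rates. If deaths were coded as events, the curve would fall, but it would then describe death while on treatment.

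**3. Death**

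Death ends treatment. Neither the figure note nor the derived variable says whether it is an event, a censoring or a competing event.

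**4. Time origin**

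The derived duration runs from a treatment start date that is not defined. Section 5.6 places "Randomization in Swedevox at or within four weeks of starting LTOT", so that date may precede allocation by up to four weeks (28 days). Section 5.3 counts treatment from randomization, and on that reading the offset is zero.

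**The case against.** The best defence is that the plan already reports withdrawal. Much of this stands. Table 1 and section 7.4 show discontinuation by arm and reason. With fixed 365-day follow-up, complete data, and deaths kept apart from stops, the proportion stopped (stops/n) equals the one-year cumulative incidence with death competing. Death does not distort that count; it shortens only the days in Table 8. A reader might infer that a difference between arms would be invisible in the report. That is true at most of Figure 1.7.

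The general sentence in 7.6 on t-tests and chi-square could be said to cover withdrawal. It applies to secondary endpoints, however, and withdrawal is not one in 4.2.2, nor is it among the categorical variables named there.

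The Figure 1.7 note may be a slip of wording in a descriptive shell. Even so, the derived variable gives no event or censoring rule that would correct it.

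Three further inferences go beyond the text:
- *UCR is bound to report this objective.* Absence from the sponsor's list points that way, but 4.1.2 assigns objectives by underlining, which the text available here does not show. The gap exists whoever does the analysis.
- *The objective is tolerability.* It is the withdrawal rate, and section 7.5 shows that withdrawal includes improved oxygenation and starting to smoke.
- *Up to 28 days of pre-randomization time enter the curve.* That depends on an undefined date; only the ambiguity is established.

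**Conclusion.** The point holds in this form: a stated secondary objective has no named outcome and no between-arm analysis, and its only time-to-event figure codes the event of interest as censoring. Followed literally with no other event coded, Figure 1.7 reads 100% in both arms at any stopping rate. The stopping proportions used above are illustrative assumptions and do not estimate how much withdrawal will occur.

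What is missing is an effect estimate with an interval, a valid time course, a rule for death and a fixed time origin. Descriptive counts by arm remain available. The primary analysis is not affected. The correction should be made, but it does not threaten the trial's main conclusion.

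**What to change.** - **Outcome.** Add time from randomization to LTOT withdrawal (Swedevox date, to day 365) to section 4.2.2 and Table 11. State that this means discontinuing LTOT and not leaving the study: the definitions in section 3 separate the two, but the Derived Variables appendix derives its withdrawals entry from the LTOT withdrawal date.
- **Analysis.** Give a between-arm estimate with a confidence interval. The Fine-Gray approach already planned in 7.6, with death as the competing event, is one suitable choice.
- **Figure 1.7.** Redefine it as cumulative incidence by arm from randomization. Stopping LTOT is the event and death competes. Patients still on LTOT at day 365, or withdrawn from the study earlier, are censored. The last group needs a place because the note to Figure 2 excepts withdrawals from complete registry data.
- **Derived variable.** Set its start date and its event and censoring rule to match.
- **Reasons.** Name the withdrawal reasons in Table 1, which now holds placeholders.

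The cost is one extra model and a change to SAP and shell wording. Swedevox already supplies the dates and reasons, so no new data are needed.
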